3.1 Study design

The study uses a randomized, double-blind, placebo-controlled, parallel group, adaptive design with variable treatment duration in approximately 2000 cognitively unimpaired participants aged 60 to 75 years, with at least one APOE4 allele (HMs or HTs) and, if HTs, with evidence of elevated brain amyloid.

Figure 3-1 Study design

The study will be conducted with three treatment arms and randomization ratio of 2:1:2 (CNP520 50 mg: 15 mg: placebo).

The treatment duration for individual participants will be variable, based on when the end of treatment epoch criteria are met, i.e. when (1) all ongoing participants have completed their month 60 assessment and (2) the overall target number of events has been reached (see [Section 3.3](#)), whichever is later. The expected maximal duration for an individual participant is 96 months (8 years).

The initial regimen is a once daily dose of 50 mg, 15 mg, or placebo throughout the full treatment epoch. If it is determined that the current doses do not provide a suitable benefit/risk profile, a single Lower Dose Regimen (LDR) will be implemented for both active treatment arms through Dose Regimen Modification (DRM) process (see [Section 5.1.1](#) and [Section 5.2](#)). This process may be triggered based on DMC recommendation and/or new data for CNP520 or other BACE inhibitors.

In case of DRM, the LDR will consist of a single lower dose regimen selected - either a 50 mg once weekly dose or a 6 mg once daily dose. Both dose regimens are expected to have a similar safety profile. The selection of the dose regimen will be based on both the timing of the DRM decision, as this may restrict options based on availability of supplies, and any further information available at that time, including PK/PD modeling, external data, etc.

The DRM activation will follow the allocation of 2:1:2 across the three treatment arms, resulting in an overall randomization ratio of 3:2 for CNP520 (arm #1 and #2) vs placebo.

The planned total number of randomized participants will not exceed $n = 2000$.

Screening

[figure not shown]

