Altogether, the screening period (part I and part II, including reflection periods when required) is expected to last about 12 weeks. The screening period can be extended on a case-by-case basis to accommodate scheduling. In such case see [Section 6.1](#) for guidance on assessments to be repeated to ensure continued eligibility during extended screening.

The assessments to be performed are listed in the assessment schedule ([Table 6-1](#)) and include assessments to be performed by the investigator/study site personnel, participant and study partner (see definition of study partner and role of key study site personnel in [Appendix 2](#)).

Treatment

Participants who are randomized to the study will receive the investigational treatment or placebo for variable treatment duration: at least 60 months, and up to an expected maximum of 96 months (see [Section 3.3](#)).

During the treatment period participants will return to the study site every three months for drug dispensing. The measurements to assess efficacy endpoints are performed at 3 months and 6 months during the first year and then every six months, and include various cognitive and neuropsychological scales with input from the study partner. Although the study partner is expected to come to the site with the participant to all relevant visits, if that proves impossible, his/her input can be obtain by telephone interview.

Safety related assessments will include regular standard assessments (e.g. eC-SSRS, vital signs physical evaluation, laboratory tests, electrocardiograms (ECGs)), as well as specific assessments related to potential CNS or other safety assessment requirements (skin photographs and pruritus evaluation, neurological evaluations, brain MRI scans for monitoring of cerebrovascular pathology and detection of ARIA) are conducted according to the schedule shown in [Table 6-1](#). Brain MRI scans will be read centrally at the Imaging Central Review Vendor, with safety reports provided to the Investigators and Novartis Medical Monitor. Guidance to the Investigators in case of new findings is provided in [Section 13.2](#).

████████████████████ and AD biomarkers; and tau PET scans (expected at the subset of sites that can participate) are performed according to the schedule shown in [Table 6-1](#).

Voluntary assessments, include amyloid PET scan and/or lumbar puncture (for biomarkers ██████████) ██████████.

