5.5.4 Instructions for prescribing and taking study treatment

Study medication CNP520 or placebo and an electronic cap (MEMS) will be dispensed at the baseline visit (Visit 201). Drug will then be dispensed at scheduled visits throughout the treatment epoch.

For dispensing visit days, participants must bring their bottle with the electronic cap on to the site (for drug accountability) and be instructed NOT to take the morning dose. Dosing on the site visit days will occur on site from the newly dispensed supply, after the visit assessments (especially blood sampling) are completed. Particular attention should be taken to schedule the ECGs about 2.5 hours after the drug administration ([Section 6.4.5](#)). In cases of technical hurdle (e.g. pharmacy off site drug delivery occurs in late morning) dispensing from the old bottle is allowed as long as it is documented and consistently implemented.

One capsule of CNP520 or matching placebo is to be taken orally once a day. (or once weekly if regimen changed), preferably at the same time of the day, i.e. in the morning, with or without food for approximately 60 months and up to an expected maximum of 84 months ([Section 3.1](#)). The last dose day for an individual participant will depend on when the target number of events is achieved. The last dose will be taken the day before treatment epoch Completion (TEC) visit. The TEC will correspond to the next planned scheduled visit after information from the sponsor that target number of events has been reached.

All kits of study treatment assigned by the IRT will be recorded/databased in the IRT.

The investigator must promote compliance by instructing the participant to take the study treatment exactly as prescribed and by stating that compliance is necessary for the participant's safety and the validity of the study. The participant and the study partner must also be instructed

to contact the investigator if the participant is unable for any reason to take the study treatment as prescribed.

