5.6 Study completion and discontinuation

5.6.1 Study completion and post-study treatment

The study will be considered completed when all the following conditions are met:

1. Target number of events has been reached
2. All individual participants have performed their scheduled month 60 or the PPW visit
3. All participants have completed their Follow-up visit

Assuming the Target number of events was reached, the Treatment Epoch will complete within 3 months of when the last participant randomized and still receiving study treatment reaches month 60. This timing will be closely monitored and all sites will be notified in the preceding 6 months to schedule the TEC visit. All assessments described in the PPW/TEC column will be completed unless they were performed in the timeframe specified in footnote 37 to Table 6-1.

Upon study completion (assuming futility was not met), participants may have the opportunity to enter an extension under a separate study, if eligible.

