²¹ Study partner required to attend visit to complete relevant assessments: ECog is self-reported by the Informant, and CDR needs to be on-site for audio recording required for central review.

²² In case sedation is required for MRI or amyloid PET scans, allow for 72 hours before cognitive assessments.

For participants who consent to the Lumbar puncture, to be done after the corresponding MRI scan at month 24 and month 60.

²³ Site should allow sufficient time to receive MRI safety interpretation prior to performing the amyloid PET scan or lumbar puncture.

²⁴ Mandatory: lumbar puncture for CSF or Amyloid PET for eligibility

²⁵ Voluntary: Ensure participant consented to the additional optional procedures

²⁶ Expected for all eligible participants in the subset of sites that can access the tau PET tracer and have the required imaging capability

²⁷ Tau PET scan will be performed after amyloid status and disclosure is completed (HTs with elevated amyloid status and HM). Results of the tau PET is not required for eligibility. Refer to [Section 6.5.3.2](#) to for conditions where tau PET is implemented In exceptional cases related to documented scheduling issues, scan can be performed within a maximum 4 weeks after the randomization date.

²⁸ Call IRT to register screening at ICF#B (as applicable), to notify screen failures/drug discontinuation as applicable.

²⁹ Randomization

³³ DVF at screening to be completed 5 days after the V103 CDR and RBANS to allow Central Review and feedback/queries closed before the PI completes the DVF (corrected scores for DMI and CDR global for the DVF). Diagnostic has to be verified as Unimpaired cognition BEFORE invasive procedures like MRI or later PET/LP.

³⁴ refer to [Section 6.1.2](#) for specific Screening lab assessments

³⁵ The LP should be performed preferably in the morning and at same time of the day before dosing. A light breakfast is allowed and should be taken 2 hours prior to LP, however, fasting is not prohibited. Participants will be required to stay in the clinic for approximately two hour after the LP for safety follow-up.

³⁶ CSF, CSF cell counts, A beta40, A beta42, tau and P-tau, NFLs, others

³⁷ Conditional assessments to be repeated upon PPW/TEC: MRI and blood AD biomarkers if last ones were more than 6 months ago, and Lumbar Puncture if last ones were more than 18 months ago

³⁸ Do not dispense at this visit as soon as target number of events is reached

³⁹ Y and Q represent Year and Quarters

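### Section 5.5.4 ties the last dose and the TEC visit to the event target alone, while Sections 3.1 and 5.6.1 and SAP 1.1.1 also require month 60; if events come fast, month-60 data are exposed

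*Protocol*

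**What the plan says.** Section 5.5.4, the dosing instruction, names one trigger. On the last dose: "The last dose day for an individual participant will depend on when the target number of events is achieved". On the visit that closes treatment: "The TEC will correspond to the next planned scheduled visit after information from the sponsor that target number of events has been reached". Earlier in the same paragraph the duration is given as "for approximately 60 months and up to an expected maximum of 84 months", with a reference to Section 3.1.

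Section 3.1 names two triggers and takes the later one: treatment ends "when (1) all ongoing participants have completed their month 60 assessment and (2) the overall target number of events has been reached". It also gives the duration as "at least 60 months, and up to an expected maximum of 96 months". The synopsis and SAP 1.1.1 repeat the two-part condition.

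Section 5.6.1 lists the event target and "All individual participants have performed their scheduled month 60 or the PPW visit" among the conditions for study completion. It adds that, once the target has been reached, "the Treatment Epoch will complete within 3 months of when the last participant randomized and still receiving study treatment reaches month 60", and that sites will be told in the preceding six months to schedule TEC.

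Footnote 38 to Table 6-1 reads "Do not dispense at this visit as soon as target number of events is reached". The visits that carry this footnote are not visible in the extracted table.

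The stated expected maximum duration also differs. It is 84 months in Section 5.5.4 and SAP 1.1.1, 96 months in the synopsis and Section 3.1, and both figures appear in Section 3.3.

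**The concern.** Sections 5.5.4 and 5.6.1 give different triggers for the same visit. If the event target is reached before the last participant's month 60, one text sends participants to TEC at their next visit and the other keeps them on treatment.

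The difference matters because participants go from TEC to a follow-up visit and are then discharged (Sections 3.1 and 3.3). A TEC before month 60 therefore removes that participant's month-60 assessment altogether, beyond any change in exposure. Change to month 60 defines the second primary endpoint and the key secondary endpoint (Table 2-1). Section 9.4.2 expects the event target to be met close to 60 months, so the plan has little margin if events come faster than assumed.

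**Working it through.** **Inputs (Protocol Sections 3.1, 6.3.1 and 9.8).** 800 participants on 50 mg, 400 on 15 mg, 800 on placebo; two-year accrual; placebo event rate 30% in 60 months, stated range 25% to 35%; hazard ratio 0.75; drop-out 30% over 60 months; target 498 events; each event confirmed at the next six-monthly visit; APCC effect size 0.20, two-sided alpha 1%.

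**Assumptions added here.** Uniform accrual, exponential event and drop-out times, the same hazard ratio in both active arms, and a six-month confirmation lag.

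**Formula.** With event hazard λ, drop-out hazard μ and θ = λ + μ, an arm of size n has expected events at T years from first randomisation (T ≥ 2) of

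E(T) = n × (λ/θ) × [1 − (e^(−θ(T−2)) − e^(−θT)) / (2θ)].

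**The plan's own figures.**
- Events needed for 50 mg versus placebo: 4 × (2.054 + 0.842)² / (ln 0.75)² ≈ 406, against 408 planned.
- Placebo λ = −ln(0.70)/5 = 0.0713; active λ = 0.75 × 0.0713 = 0.0535; μ = 0.0713. At T = 7, E = 229.5 (placebo) + 180.3 (50 mg) + 90.2 (15 mg) = 500.0, against 228 + 180 + 90 = 498 planned.

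Both reproduce, so no sample-size figure is in dispute.

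**When the 498th confirmed event falls.** Two confirmation models were used:
- (a) a plain six-month delay, solving E(T − 0.5) = 498;
- (b) the same delay with drop-out during it, solving e^(−0.5μ) × E(T − 0.5) = 498, where e^(−0.0357) = 0.965.

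The last participant enters at two years and reaches month 60 at 7.0 years. The share of the cohort by entry date that is short of month 60 on the day of the target is (7 − T)/2. If TEC falls a full three months later, which is the visit spacing, the share is (6.75 − T)/2.

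| Placebo rate, HR | Model | T (years) | Last participant at month | Short on the day | Short with 3 more months |
|---|---|---|---|---|---|
| 30%, 0.75 (design) | a | 7.46 | 65.6 | 0% | 0% |
| 30%, 0.75 (design) | b | 7.80 | 69.6 | 0% | 0% |
| 35%, 0.75 | a | 6.22 | 50.7 | 39% | 26% |
| 35%, 0.75 | b | 6.47 | 53.7 | 26% | 14% |
| 30%, 1.0 | a | 6.35 | 52.3 | 32% | 20% |
| 30%, 1.0 | b | 6.61 | 55.3 | 19% | 7% |
| 25%, 0.75 | a | 9.44 | 89.2 | 0% | 0% |

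Even with no confirmation lag, the design case gives 6.96 years, the last participant at month 59.6 and 1.8% short.

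The last column is closest to the wording of Section 5.5.4: a participant already past month 57 has month 60 as the next three-monthly visit. The 39% allows no wait for that visit and is an outer bound.

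**APCC power (normal approximation to the plan's t-test).** Power = Φ(0.20 × √(n/2) − 2.576), n per arm with a month-60 value.
- Planned: n = 800 × 0.70 = 560; 3.347 − 2.576 = 0.771; 78.0%.
- 14% short: n = 560 × 0.86 = 482; 3.104 − 2.576 = 0.528; about 70%.
- 26% short: n = 560 × 0.74 = 414; 2.877 − 2.576 = 0.301; about 62%.

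**The case against.** The best defence is that Section 5.5.4 is not a free-standing stopping rule. Its paragraph speaks of about 60 months and cites Section 3.1. TEC also waits for information from the sponsor, and Section 5.6.1 tells the sponsor to time TEC around the last on-treatment participant's month 60. Early cut-off would need the sponsor to act against Sections 3.1, 3.3 and 5.6.1. This makes the loss less likely in practice, but it does not remove the contradiction. An approximate duration is not a minimum, and Section 3.3 itself starts the completion process, including scheduling each participant's end of treatment, when the event target is anticipated.

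Four further points stand and limit the concern:
- A reader might infer that the plan cuts off the APCC endpoint as designed. It does not: in the design case nobody is short of month 60 once confirmation is counted.
- A reader might take footnote 38 as a second instance. That cannot be confirmed. If it marks only visits from month 60 onward, it conflicts with nothing.
- Counting events at first diagnosis would put the 35% scenario at 5.72 years with 64% short. The protocol counts only confirmed events, so that figure does not apply.
- The t-test gives no credit for earlier visits. The primary APCC analysis is an MMRM that uses them, so its power would fall by less.

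**Conclusion.** The contradiction is real and sits in Section 5.5.4. Its consequence is conditional: none to speak of at the design assumptions or at a 25% event rate, and material if events come faster. At 35% with hazard ratio 0.75, about 14% to 39% of the cohort would have TEC before month 60. The 14% to 26% part of that range brings APCC t-test power to between about 70% and 62%. At the design event rate with no drug effect, 7% to 32% would be affected. All of these shares rest on the modelling assumptions listed with the calculation and are taken by entry date, before drop-out.

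Nothing here bears on the reported results. Treatment was stopped in July 2019, and SAP Sections 2 and 2.5.4 drop the month-60 inferential analyses because no month-60 data exist. The fault is one of the plan as written.

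**What to change.** Reconcile Section 5.5.4 with Sections 3.1 and 5.6.1 so that every passage that triggers TEC or the end of dispensing states the same condition or conditions. Which condition governs is for the sponsor to settle; this point does not propose one.

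In the same edit, check which visits carry footnote 38 of Table 6-1 and whether it conflicts, and bring the 84-month and 96-month statements of expected maximum duration into agreement across the synopsis, Sections 3.1, 3.3 and 5.5.4, and SAP 1.1.1.

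The cost is a few sentences of wording. No sample size, event target or analysis model changes. As the trial has ended, the practical use is for any protocol that reuses this text.

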5.5.5 Permitted dose adjustments and interruptions of study treatment

Change in frequency of dosing by site or participant are not permitted. In case a daily dose was omitted, it can still be taken until approximately 6 hours after the usual once daily administration time, otherwise it should be skipped and treatment resumed next day at regular time.

In the case that the timing of the site visit deviates from the regular time that the participant takes the study medication, the study medication can still be administered at the site visit if it is within ± 6 hours of the usual time. I.e. the dose can be given 18 to 30 hours after the previous dose.

If the DRM is activated for a one weekly administration and a weekly dose is missed, it can still be taken within 3 days (72 hours) of the missed regular weekly dosing day. Otherwise the dose should be skipped and treatment resumed at the regular day of the next week.

In the case that one or more dose(s) are missed, study treatment should resume as soon as possible. Any missed doses should be recorded on the Dosage Administration eCRF page. Also see [Section 5.6.2](#) for reasons to discontinue or suspend study treatment.

Investigational treatment should be suspended for participants:

- who no longer have a study partner for a period of > 3 months; when the replacement study partner is identified, study treatment can be resumed for the participant
- during the time they are taking medications listed in [Table 5-1](#) leading to temporary suspension of investigational treatment (e.g. for an acute condition)
- develop a condition/decision leading to suspension of study treatment at any time for any reason
- who request temporary suspension of study treatment

Study treatment can be resumed at any point later in the study after the condition above has resolved, and participant attended the scheduled visits / assessments per protocol during the duration of the suspension.

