A non-stratified log-rank test will be conducted to compare estimates of the hazard functions of the treatment arms.

In order to understand the potential longitudinal difference in the rate of disease progression by genotype, a longitudinal Cox PH model will be implemented as an important primary supportive analysis. This will be done by including the additional interaction term treatment arm × genotype × visit window.

Excluding data after discontinuation of study drug in APCC

As with the primary analysis method (MMRM) for APCC, this analysis will assume missing data to be MAR.

Within this analysis, the following data will be excluded (regarded as missing though it is available) and thus implicitly assumed to be MAR:

- Data retrieved from participants remaining in the treatment epoch beyond 12 weeks after permanent study drug discontinuation
- For intermediate study drug interruptions lasting longer than 12 weeks, off-drug APCC data during this period, but beyond the abovementioned 12 weeks. Assessments subsequent to resuming drug administration will be included in the analysis.

In addition to this analysis, the same tipping point, controlled imputation and ‘copy reference’ sensitivity analyses as planned for the primary analysis will be conducted, but additionally excluding the off-treatment data to be missing as mentioned above.

Other analyses on the endpoint APCC

The primary analysis of the APCC test score will be supported by the following important primary supportive analysis: An MMRM is based on the same assumptions as the primary analysis model and includes the same factors, but also including the additional interactions (and underlying factors)

- baseline hippocampal volume | visit window
- genotype (HM, HT) | visit window | treatment

The primary analysis will be supported by an MMRM similar to the primary model, but using time as a continuous factor. The interpretation of results from the primary analysis will also be supported by the investigation of change in treatment effects over distinct time periods.

Potential drug-drug-interaction (DDI)

Potential PD-mediated DDIs with frequent concomitant medications may include the use of cholinesterase inhibitors in terms of transient interaction with cognitive readouts.

Treatment interaction with CNP520 will be assessed as follows:

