For efficacy parameters: In case of competing assessments within a visit window, the assessment value closest to the scheduled visit day will be used. In case of equal distances, the earliest assessment value will be used. Visit window will not be applicable for TEC and EoS.

For safety parameters: In case of competing assessments within a visit window, the worst assessment value within the visit window will be used. This rule also applies for worsening in cognition as a safety measure.

Listings will include all assessments, sorted by date of assessment, flagging unscheduled visits. The listings will include analysis windows and corresponding flags to indicate the assessment's inclusion in the analysis.

Treatment Epoch Completion (TEC) and End of Study (EoS) and other points in time of interest

TEC is the end of treatment phase visit (i.e., visit 299) that will be completed for all participants after discontinuation of treatment. The same visit will also be completed in case of PPW. PPW is the premature study withdrawal.

EoS is a Follow-up visit scheduled after TEC/PPW, per urgent safety measure (USM) on 11-Jul-2019, and its follow-up letter dated 12-Dec-2019, Modified EoS visits can be scheduled anytime after receipt of this notification but no later than 15-Mar-2020. (i.e. the requirement from 11 July 2019 USM for the 6 month timeframe between modified TEC and mEoS visits is no longer required.).

Participants who were attending study visits (i.e., continuing in the study) but already off-treatment at time of USM were to come for EoS straight (no TEC required).

An assessment will be on treatment if it is before or at last day on study drug + 31 days. The last assessment before or at last day on study drug + 31 days will be referred to as "last on treatment" assessment. The last assessment after last day on study drug + 31 days will be referred to as "last off treatment" assessment. For deriving "last on treatment" or "last off treatment", last assessment date of RBANS will be used. That means, to derive the last on treatment and last off treatment for all the parameters, regardless of their actual assessment

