dates, RBANS last assessment date will be used as reference date. Note: the “last on treatment” and “last off treatment” flag will be created for each participant at visit level (not at the individual assessment level). If there is missing RBANS assessment at the specific visit, then date of the first day corresponding to that visit (i.e. non-missing assessment of that parameter under consideration) will be used to derive the “last on/off treatment” assessment.

Note: On treatment is a period from first dose to last dose + 31 days.

For example:

1. If a participant has the last dose on 13-Jul-2019, then “on treatment” period would span from first dose to 13-Jul-2019 + 31 days.
2. If a participant has the last dose on 09-Apr-2019, then “on treatment” period would span from first dose to 09-Apr-2019 + 31 days.

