2.4 Treatments (study treatment, rescue medication, concomitant therapies, compliance)

2.4.1 Study treatment / compliance

The duration of exposure to study drug is defined as the time (in days) from the first study drug administration to last study drug administration + 31 days.

The duration of exposure will be calculated as

(last dose date + 31 days) – first dose date + 1.

Duration of exposure to CNP520 will be summarized as continuous variable (in days) and categorical variable, using categories ≥ 1 day (any exposure), ≥ 3 months, ≥ 6 months, ≥ 1 year, ≥ 1.5 years.

For each treatment group, the participant-years will be calculated as

(sum of the durations of exposure for all participants in the group)/365.25) and will be summarized.

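### SAP 2.1.1 ignores dosing gaps, so drug-free assessments made during a suspension that is later resumed count as on treatment

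*Protocol*

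**What the plan says.** Protocol 5.5.5 lists several grounds for suspending drug: no study partner for more than 3 months, temporary use of certain prohibited medications, any other condition or decision, and participants "who request temporary suspension of study treatment". On resumption it says "Study treatment can be resumed at any point later in the study after the condition above has resolved", on condition that the "participant attended the scheduled visits / assessments per protocol during the duration of the suspension". It states no maximum duration.

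SAP 2.1.1 takes the last dose to be the final intake overall. It then says "An assessment will be on treatment if it is before or at last day on study drug + 31 days", and its note reads "On treatment is a period from first dose to last dose + 31 days". SAP 2.4.1 measures exposure "from the first study drug administration to last study drug administration + 31 days". Neither section mentions interruptions.

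Protocol 9.4.4 did have an interruption rule, in supportive analyses only. For APCC it set aside "For intermediate study drug interruptions lasting longer than 12 weeks, off-drug APCC data during this period, but beyond the abovementioned 12 weeks", and it had a parallel rule for the time-to-event endpoint. SAP 2.5.6 marks supportive analyses as not applicable, and SAP Section 4 lists them as not performed. No interruption rule replaces them.

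**The concern.** The protocol foresees drug-free periods with assessments inside them, since attending visits is a condition for restarting. The SAP's on-treatment label uses only the first and final dose dates, so once drug is resumed the whole gap is labelled on treatment. The 31-day wash-out allowance is applied after the final dose but not after the last dose before a gap.

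This matters because the lead analysis of the abbreviated report is worsening in cognition and its reversibility (SAP 2.5 and 2.5.1). Three kinds of output rely on the label:

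- the on-treatment Kaplan-Meier analyses of first change in diagnostic classification and of first RBANS total decrease of at least 14 points (SAP 2.5.4);
- the proportion worsening at any visit up to and including *last on treatment* (SAP 2.5.1);
- the *last on treatment* value and changes measured from it (SAP Section 2).

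The rationale for protocol Amendment 03 reports reversal of worsening in visits 1 to 8 weeks after wash-out. Drug-free values filed as on-drug could therefore blur the contrast these outputs are meant to show.

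**Working it through.** **Inputs.** Half-life about 150 hours (protocol 1.1 and 3.3). Carry-over of 31 days, stated as 5 half-lives (SAP 2.8.1). Exposure = (last dose date + 31) − first dose date + 1 (SAP 2.4.1). mSAF threshold of 3 months' exposure (SAP 2.2), taken here as 91 days (assumption). All dosing histories below are assumed, because the documents give none.

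**1. The SAP's own figure.** 5 × 150 / 24 = 31.25 days, which reproduces the stated 31.

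**2. Drug remaining d days after a dose,** 0.5^(24d/150):
- d = 31: 4.96 half-lives, 3.2%
- d = 61: 9.76 half-lives, 0.1%
- d = 91: 14.56 half-lives, 0.004%

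Days 1 to 31 of a gap are covered by the SAP's carry-over allowance. From day 32 until resumption the participant is drug-free by the same criterion. If drug is never resumed, final dose + 31 days closes the window correctly.

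**3. How a gap visit becomes *last on treatment*.** Dosed Days 1–30, suspended Days 31–120, dosed Days 121–125. The SAP window ends on Day 125 + 31 = Day 156. A Week 13 RBANS on Day 91 is 91 − 30 = 61 days after the previous dose. If no RBANS is done after Day 91 and by Day 156 (the next is scheduled for Week 26, Day 182), this drug-free result is the *last on treatment* value. Any later RBANS by Day 156 would replace it.

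**4. Exposure for one participant,** 91 days dosed, a gap, 91 days dosed. Only gap days beyond 31 are removed:

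| Gap (days) | SAP exposure | Segment-based | Drug-free share of SAP exposure |
|---|---|---|---|
| 45 | 227 + 31 = 258 | 258 − 14 = 244 | 5% |
| 91 | 273 + 31 = 304 | 304 − 60 = 244 | 20% |
| 182 | 364 + 31 = 395 | 395 − 151 = 244 | 38% |

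**5. mSAF membership.** Single doses on Days 1 and 60 give SAP exposure (60 + 31) − 1 + 1 = 91 days, which meets the threshold. By segments it is 32 + 32 = 64 days, which does not. The history in step 3 gives 156 days by the SAP and (30 + 31) + (5 + 31) = 97 by segments, so that participant is in the mSAF either way.

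**The case against.** The strongest reply is that the effect needs a narrow sequence. Drug must be resumed, the assessment must fall on or after day 32 of the gap, and, for *last on treatment*, no later RBANS may fall within the window. Some gaps are limited: protocol 5.5.5 asks that dosing resume as soon as possible after missed doses, and chronic use of most Table 5-1 medications leads to discontinuation, which closes the window properly. Five of the seven effect-size time points in SAP 2.5.1 (Weeks 13, 26 and 52, TEC, EoS) do not use the label, and the outputs are descriptive. The programming specifications and table shells, which are not available here, could hold a rule. All of this stands. It bears on size and does not remove the misclassification in the SAP definitions.

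Three stronger readings are tempting and not supported:

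- *Exposure-adjusted adverse event rates are simply lowered.* The treatment-emergent window in SAP 2.8.1 also runs to 31 days after the last dose, so gap events are in the numerator just as gap time is in the denominator. The rate moves towards the drug-free rate, which need not mean down.
- *Protocol 9.4.4 would already have excluded these visits.* Its limit is 12 weeks (84 days), so the 61-day visit in step 3 would be kept. Its analyses were supportive only, and the protocol's primary analyses did not exclude off-drug data. Using 31 days for gaps extends the SAP's own criterion and does not restore the protocol rule.
- *The trial-level error can be estimated.* If 5–15% of participants suspended for 13–26 weeks within a year and all resumed, exposure would be overstated by 0.05 × (91 − 31)/364 = 0.8% to 0.15 × (182 − 31)/364 = 6.2%. Those rates are assumptions, so the range shows sensitivity only.

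**Conclusion.** The point holds in limited form. When drug is resumed, assessments from day 32 of a gap until resumption are drug-free by the SAP's five-half-life criterion but are classed as on treatment. They enter the on-treatment time-to-event analyses and the any-visit worsening summary, and under the condition in step 3 they supply the *last on treatment* value. mSAF membership changes only in particular histories such as that in step 5.

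The size cannot be determined, because neither document gives the number or length of suspensions. It may be small, since the SAP notes that very few participants had active-treatment data beyond one year. The label does not affect scheduled by-visit summaries. A reader might infer that protocol 5.5.5 is itself at fault. It is not: it makes the gaps possible, and the omission is in the SAP.

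**What to change.** In SAP 2.1.1, define on treatment as the union of dosing segments from the Dosage Administration eCRF, each extended by 31 days. Assessments outside these segments should not qualify as *last on treatment*, should not count in the any-visit summary that ends there, and should be left out of the on-treatment time-to-event analyses.

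If exposure, participant-years and mSAF membership (SAP 2.4.1 and 2.2) are also computed from segments, apply the same segments to the treatment-emergent window in SAP 2.8.1. Otherwise gap events would stay in the numerator while gap time left the denominator, and rates would be pushed up. List the change in SAP Section 4.

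The cost is SAP wording and programming, slightly smaller exposure totals and fewer on-treatment assessments. Protocol 5.5.5 already requires missed doses to be recorded, so no new data are needed. The SAP revision history shows on-treatment analyses being added by addendum after database lock; this change could be made the same way, with its timing stated. No change to the clinical suspension rule is proposed.
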